## 2.7 Statistical Analysis and Sample Size Justification

This study is a pilot protocol. Our goal is to enroll a total of 90 subjects (30 Duke, 60 Cleveland).

For the primary analysis: If we anticipate a loss of up to 15% of subjects for various reasons beyond our control so that we will end up with about 76 subjects for full analysis. Using G\*Power to perform a sample size calculation with 76 subjects (38 vaccinated and 38 un-vaccinated) and an analysis comparing these two groups at the 3 time points to test Hypothesis 1 using a 2 x 3 Repeated Measures ANOVA with power 0.8 and  $\alpha$  error 0.05 we can detect an effect size of 0.27. For independent t-tests analyzing mean differences at each individual time point we would be able to detect an effect size of 0.58. For both of these types of analyses our power is near a medium effect size. We do not have preliminary data in this population for a precise sample size calculation. The data from this pilot study will inform the sample size for a larger future study.

Fold change will be the primary immune analysis and will be calculated for each individual subject based on their day 0 SFU on ELISPOT. Fold change will be calculated at each time point (chemo initiation, during chemo, 3 months post). This will take place in both the vaccinated and non-vaccinated groups. As this model reflects a 2 group by 3 time point design, our initial overall assessment of the data will use a 2X3 Repeated Measures ANOVA (RMANOVA) to identify mean differences between groups, within time mean differences, and the interaction between groups and time to identify if the trends in the means over time is different for groups (vaccine vs. no vaccine). For the next step to gain a better understanding of how well the vaccine works at each time point (Hypothesis 2-4), we will use independent samples t-tests to analyze group mean differences at each time point separately to gain a better understanding of how the groups may be different at chemotherapy initiation, during chemotherapy, and at 3 months post-chemotherapy. Additionally, if we identify a significant interaction between group and time points, we will run follow-up RMANOVAs for each group separately to identify not only mean difference over time, but also linear (e.g. a steady increase or decrease in mean scores over time) and quadratic (e.g. a high mean scores at chemotherapy initiation, followed by a decline in mean score during chemotherapy, followed by a steady increase in mean score at 3 months post-chemotherapy) trends in the means over time for each group. Violations of the assumptions for each analysis will be tested and the data will be transformed or the nonparametric equivalence analysis will be used when appropriate.

[name] is the director of the Cleveland VA's core statistical center. He is an ongoing Co-investigator with effort on one of [name] R01 grants. He will perform the statistics for this study.

Safety and tolerability will be assessed by statistical and clinical review of all safety data collected throughout the study. All subjects who are vaccinated and provide any safety follow-up will be included in safety analyses and summaries. To provide an overall assessment, the incidence rate for the vaccination group and no-vaccination group, the risk difference between the two groups and the associated 95% CI will be provided for broader safety measures such as the proportions of the subjects with any: adverse experiences; injection-site adverse experiences; systemic adverse experiences; serious adverse experiences; or vaccine-related serious adverse experiences after vaccination.

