2. We hypothesize that the fold increase in Varicella Zoster Virus (VZV)-specific immunity in subjects with solid organ tumors that were given ZOSTAVAX at least 14 days prior to initiation of chemotherapy will be higher than the control group that is not vaccinated.
3. We hypothesize that immediately before the second cycle of chemotherapy VZV-specific immunity will be higher in those subjects that received ZOSTAVAX prior to chemotherapy than those that were not vaccinated.
4. We hypothesize that at 3-18 months post-chemotherapy VZV-specific immunity will be higher in those subjects that received ZOSTAVAX prior to chemotherapy than those that were not vaccinated.
5. We hypothesize that ZOSTAVAX is safe if given to subjects with solid organs tumors at least 14 days prior to initiation of chemotherapy or surgery followed by chemotherapy.

10. Describe the means of analyzing the data and evaluating the results.

- *State the anticipated methods to be used for analysis and interpretation of the data.*
- *The methods must compliment the design of the study and the nature of the data which is being collected.*

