A portion of the sample may be sent to our collaborators at University of Pennsylvania (Drs. [name] and [name]), or Vaccine and Gene Therapy Institute in Port-St-Lucie, FL ([name], coming to CWRU this Fall to join our faculty), and Merck's immune assay unit (Swiftwater, PA) as each of these collaborators perform assays that we do not perform at the VA in the [name] laboratory. Any samples that are sent will be coded with no personal identifiers. The cells going to Penn will have advanced T cell marker analysis and cloning, to [name] they will have transcriptomic analysis, and to Merck they will have anti-VZV glycoprotein ELISA performed. Samples will be destroyed in Cleveland and at the other sites after the assays are performed.

11. Provide a BRIEF DESCRIPTION of how the estimated number of study subjects needed for this research was determined

- *If this is a quantitative study provide the method of determining sample size estimates.*
- *If multiple studies are planned provide a power analysis or justification for each one.*

This is a pilot study so precise sample size calculations are not possible since the data do not exist yet to determine this. Obtaining this pilot data is one of the key purposes of this study. For the primary analysis: If we anticipate some loss of subjects for various reasons beyond our control so that we hope to end up with about 76 subjects for full analysis after initially enrolling 90 subjects. This is based a projection of receiving up to 30 coded samples from our collaborator [name] at Duke University who is running a similar study at that site and initially enrolling 60 from Cleveland. Using G*Power to perform a sample size calculation with 76 subjects (38 vaccinated and 38 un-vaccinated assuming some loss due to lack of all 4 timepoints) and an analysis comparing these two groups at the 3 time points to test Hypothesis 1 using a 2 x 3 Repeated Measures ANOVA with power 0.8 and α error 0.05 we can detect an effect size of 0.27. For independent t-tests analyzing mean differences at each individual time point we would be able to detect an effect size of 0.58. For both of these types of analyses our power is near a medium effect size. The data from this pilot study will inform the sample size for a larger future study.

12. The research involves the following procedures conducted by and for what purpose:

[figure not shown]
PROCEDURE	PERFORMED BY:		PROCEDURE IS:	

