30 ZOSTAVAX

30 no vaccine

The Duke University site will have 15-ZOSTAVOX and 15 no vaccine

N/A SINGLE SITE

22. Duration of individual subject participation

Provide answers for each cohort including normal controls; (patients, family members, treating physicians,). 5 years or less depending on the duration of their chemo.

Chart/record review N/A

23. Age range of subjects

- provide answers for each cohort, including normal controls:

Adults 18 years or greater

Specific age range (list age range): 50 years and older for both cohorts

Children –waiver from VACO: attached pending- provide submission date:

**Contact AO/Research [contact] for guidance..

24. Which of the following will be recruited or reviewed for this study (check all that apply)?

Veteran Inpatients

Men

Veteran Outpatients

Women

Veteran Families

*Normal volunteers

*Non-Veterans; Provide justification

*According to VHA Handbook 1605.04 Notice of Privacy Practices VHA must provide a copy of its VHA Notice of Privacy Practices to all non-Veteran patients (e.g., active duty personnel or those seeking care in humanitarian circumstances) receiving care or treatment at a VHA health care facility or non-Veteran research subjects enrolled in an approved VHA research study with clinical trials. VA Form 10-0483 Acknowledgement of the Notice of Privacy Practices should be signed by the non-Veteran research subject at the time of consent and given a copy of the Notice of Privacy Practices. Once the Acknowledgement Form is signed please send a copy to the Privacy Officer. If additional information is needed please contact your Facility Privacy Officers [name] or [name] [contact] / [contact] [contact] / [contact].

25. Which vulnerable population(s) will be TARGETED for recruitment in this study:

- Indicate only those populations that are specifically targeted for the research described in this document.
- *It is not necessary to check any box if, for example, your study will include a full range of subjects, some of whom may be elderly or subjects who might incidentally be employees.*

- N/A Chart Review (proceed to Item 30)
- NONE (proceed to Item 26)
- Medical students, house staff, or Employees of the VAMC or Case
- Pregnant Women OR Women who are Breastfeeding, Human Fetuses, or Neonates
- Children – Complete Section 14 “Children as Research Subjects”
- Prisoners (The LSCDVAMC does not conduct research involving prisoners)
- Targeting Persons over Age 65

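### The detectable effect of 0.58 for the per-time-point t-tests matches a one-sided test that the plan does not declare; two-sided at 0.05 it is 0.65

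*SAP*

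**What the plan says.** SAP 2.7 plans for "76 subjects (38 vaccinated and 38 un-vaccinated") in the full analysis. Protocol item 11 gives the same split, described as "38 vaccinated and 38 un-vaccinated assuming some loss due to lack of all 4 timepoints". Both documents then quote a detectable effect of 0.27 for the overall test of Hypothesis 1, obtained "using a 2 x 3 Repeated Measures ANOVA with power 0.8" and an alpha of 0.05. The next sentence turns to the t-tests: "For independent t-tests analyzing mean differences at each individual time point we would be able to detect an effect size of 0.58". It adds no inputs.

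The t-tests are the named analysis for Hypotheses 2 to 4. The analysis text (SAP 2.7 and protocol item 10) says "we will use independent samples t-tests to analyze group mean differences at each time point separately", to learn how the groups may differ at each point. The hypotheses themselves, in protocol item 9, have a direction. Hypothesis 3, for example, is that "immediately before the second cycle of chemotherapy VZV-specific immunity will be higher in those subjects that received ZOSTAVAX" than in those not vaccinated. Nothing in either document says whether the t-tests are one-sided or two-sided.

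**The concern.** A detectable effect has a meaning only with its alpha, power, sample size and sidedness. Here sidedness is absent, and the figure given is the one that a one-sided test produces. The description of the tests has no direction, so a reader would ordinarily take them as two-sided at 0.05. That reader would believe the t-tests have 80% power at 0.58 when they have less.

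There is also a practical ambiguity. A result that favours vaccine with a two-sided p between 0.05 and 0.10 would be significant under one reading and not under the other. With sidedness left open, that choice could be made after the data are seen. The plan also says that the pilot will inform the size of a larger trial, so the figures carried forward should be correctly labelled.

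**Working it through.** **Inputs**

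- Analysed subjects: 38 per arm (SAP 2.7, protocol item 11).
- Upper limit: 45 per arm, if every enrolled subject contributes at a time point. SAP 2.7 says "Our goal is to enroll a total of 90 subjects (30 Duke, 60 Cleveland"). Protocol items 20 and 21 give 30 + 30 in Cleveland, and "The Duke University site will have 15-ZOSTAVOX and 15 no vaccine". So 30 + 15 = 45 per arm.
- Loss of up to 15%: 90 × 0.85 = 76.5, hence about 76.
- Power 0.8 and alpha 0.05: stated for the repeated-measures ANOVA. Applying them to the t-tests is an assumption, though the natural one.

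**Method**

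Exact power of the two-sample t-test with n per arm, from the noncentral t distribution: df = 2n − 2 and noncentrality = d × √(n/2). The detectable effect is the d at which power equals 0.80.

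**Reproducing the plan's figure, n = 38 (df = 74)**

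| Test at alpha 0.05 | Detectable d at 80% power | Power at d = 0.58 |
|---|---|---|
| One-sided | 0.576 | 80.5% |
| Two-sided | 0.651 | 70.4% |

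At d = 0.58 the noncentrality is 0.58 × √19 = 2.53. The one-sided value rounds to the stated 0.58. The smallest n per arm that gives one-sided 80% power at 0.58 is exactly 38 (37 gives 79.6%).

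**Could the no-loss sample size explain it? n = 45 (df = 88)**

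| Test at alpha 0.05 | Detectable d at 80% power | Power at d = 0.58 |
|---|---|---|
| One-sided | 0.528 | 86.1% |
| Two-sided | 0.597 | 77.7% |

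Neither value is 0.58.

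**Could rounding explain it?** A printed 0.58 covers 0.575 to 0.585. Over that range two-sided power is 69.6% to 71.1% with 38 per arm and 77.0% to 78.4% with 45 per arm. It does not reach 80%.

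**Sample size for two-sided 80% power at 0.58:** 47 per arm gives 79.5% and 48 per arm gives 80.3%. So 2 × 48 = 96 analysed subjects are needed, against 90 to be enrolled.

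**Where sidedness changes the reading of a result:** the smallest significant observed standardised difference is t_crit × √(2/n). With n = 38 this is 0.382 one-sided and 0.457 two-sided. An observed difference favouring vaccine between about 0.38 and 0.46 is significant under one rule only.

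**The case against.** The strongest reply is that no calculation error has been shown. The stated inputs give 0.58 at exactly 38 per arm under a one-sided test, and the t-tests serve three hypotheses that all predict higher immunity with vaccine. On that view the figure fits the hypotheses and lacks only a label, and the two-sided shortfall follows from a reading that the documents do not state. A two-sided remedy would then be the reviewer's preference.

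Much of this stands. A one-sided test is a plausible intent, and the shortfall is conditional on two-sided testing. But a directional hypothesis is not a rejection rule. The text that describes the tests speaks only of differences between groups, and neither document declares a one-sided test.

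A second reply is that 0.58 also arises with 38 per arm at two-sided alpha 0.10 (0.576), or at two-sided 0.05 with 70% power (0.577). That is correct, so the one-sided match is unique only once power 0.8 and alpha 0.05 are carried over. The plan states neither alternative. The first uses the same upper-tail threshold as one-sided 0.05, and the second is the shortfall itself.

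A third reply is that this matters little. The study is a pilot, the t-tests follow the overall ANOVA, and the plan allows transformation or nonparametric methods, so any t-test figure is approximate. This also stands, and it limits the size of the point. It does not make an unlabelled figure right.

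**Conclusion.** The concern holds. Given 38 per arm, power 0.8 and alpha 0.05, the stated 0.58 is a one-sided figure, and the plan does not declare one-sided tests. If the tests are run two-sided at 0.05, the detectable effect is 0.65, or 0.60 with no loss at all. Power at 0.58 is then about 70% to 78% rather than 80%, and no number of analysed subjects up to the 90 enrolled delivers the stated figure.

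The conclusion rests on carrying power and alpha over from the preceding sentence, on equal arms, and on no multiplicity adjustment across the three time points. It does not establish that the authors made an arithmetic error. The consequence is modest, but the point should be fixed before analysis, because a choice of sidedness made after seeing the data would not be credible.

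**What to change.** In SAP 2.7 and protocol item 11, state the sidedness of the t-tests before analysis and give the figure that matches.

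- **Preferred:** declare two-sided tests and replace 0.58. Suggested wording: *The t-tests are two-sided at alpha 0.05; with 38 per arm they detect d = 0.65 with 80% power (0.60 if all 45 per arm contribute).*
- **If one-sided tests of Hypotheses 2 to 4 were intended:** declare and justify one-sided alpha 0.05, and label 0.58 as one-sided.

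The cost is one sentence and one figure, or one label, in two documents. Enrolment, visits, assays, the ANOVA figure and the description of the effect as near medium can all stay as they are. The only downside is a slightly less favourable stated figure if two-sided tests are declared.

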Surgical procedure or Specimen removal during surgery				
Tissue banking (complete Section 12)				
Use of pre-existing tissues/specimens				
Other (list):				

- **Standard of care procedures are procedures performed in the course of normal medical care.*
- ***Research Procedures are performed for the purposes of this research alone.*

13. Please describe the research design and all study related procedures.

- Describe ALL PROCEDURES ASSOCIATED WITH THIS RESEARCH. This includes standard of care and research procedures.
- For complex studies please include diagrams and tables. Be sure to describe when each procedure will be performed. Be sure to provide information for each cohort, including normal controls.

Study participants based on the inclusion and exclusion criteria listed below will be recruited from the Oncology clinics and medical services of the Cleveland VA. The study oncologist will review the study with them. Subjects that consent will be randomized to one of the two arms, vaccine or no vaccine. Individuals will undergo blood draws for immunologic assays according to time points depicted in the figure below. Each blood draw (25 ml each) has been timed to follow routine clinical monitoring as ordered by the oncologist for maximum feasibility.

- The first blood draw will be at the time of consent into the study. We anticipate this time to be the first visit with the oncologist. They will receive ZOSTAVAX on that day if they are in that arm of the study.
- The second blood draw will be on the day of chemotherapy initiation, no earlier than 14 days post-vaccination. This will be longer than 14 days for example when there is surgery between the vaccination and the start of chemotherapy.
- The third blood draw will be at the start of the second chemotherapy cycle.
- The fourth blood draw will be 3-24 months post chemotherapy cessation. The timing of the final blood draw is based on cessation of chemotherapy and not any concurrent radiation therapy that would be also completed by the 3-6 month post-chemotherapy sampling.

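### The RMANOVA time and group-by-time tests need sphericity, which the visit spacing makes doubtful, and the remedies named in SAP 2.7 do not reliably deal with it

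*SAP*

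**What the plan says.** SAP 2.7 makes the 2x3 RMANOVA of fold change the first overall analysis, and its sample size paragraph ties that model to Hypothesis 1. The model tests group, time and "the interaction between groups and time to identify if the trends in the means over time is different for groups". The interaction also acts as a gate: "if we identify a significant interaction between group and time points, we will run follow-up RMANOVAs for each group separately".

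The plan commits to testing the assumptions of each analysis. Its response to a violation is that "the data will be transformed or the nonparametric equivalence analysis will be used when appropriate". Protocol item 10 carries the same sentence. Neither document mentions sphericity, an epsilon correction, a multivariate test or a mixed model.

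Protocol item 13 sets the timing. Draw 2 is on the day chemotherapy starts. For the next two draws: "The third blood draw will be at the start of the second chemotherapy cycle"; "The fourth blood draw will be 3-24 months post chemotherapy cessation". SAP 2.7 puts the last visit at 3 months after chemotherapy. That difference is a separate matter, because the gaps are unequal either way.

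**The concern.** With three visits, the univariate F tests for time and group-by-time hold their level only if the variances of the three pairwise visit differences are equal. The gap between the first two analysed draws is one cycle. The next gap is the rest of chemotherapy plus at least 3 months. If correlation within a subject fades with time, the early pair is more alike than either is to the last draw, and sphericity fails. The SAP's own quadratic example (high, then lower, then rising) also expects the means to move. For a ratio measure that often changes the variances too.

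When sphericity fails, the uncorrected test rejects too often. The interaction is the plan's only test of whether the arms' trajectories differ, and it alone opens the within-arm RMANOVAs, whose time tests carry the same assumption. The pilot is meant to inform a larger study, so a spurious interaction could mislead that design.

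**Working it through.** **Inputs from the documents.** 76 analysed subjects, 38 per arm, three time points, alpha 0.05 and power 0.8 (SAP 2.7); visit timing (Protocol item 13). No variance or correlation is given, and SAP 2.7 says there are no preliminary data in this population. Every covariance below is therefore an assumption.

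**The plan's own figure.** SAP 2.7 gives a detectable effect of 0.27 for the RMANOVA without saying for which term. Take m = 3 visits and an assumed correlation ρ = 0.5.
- Between-group effect: λ = f²·N·m/(1+(m−1)ρ) = 0.27²·76·3/2 = 8.31 on F(1,74). Power is 81.2%, and 80% power needs f = 0.266. The figure reproduces.
- Interaction, standard definition: λ = f²·N·m/(1−ρ) = 0.27²·76·3/0.5 = 33.2 on F(2,148). Power is above 99.9%, and 80% power needs only f = 0.147. The figure does not reproduce.

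The stated 0.27 thus fits the group main effect, which does not need sphericity.

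**Epsilon.** Let a be the correlation between draws 2 and 3, and b that of each with draw 4. With equal SDs, the two orthonormal visit contrasts have variances l1 = 1−a and l2 = 1 + a/3 − 4b/3 and are uncorrelated. Then ε = (l1+l2)²/[2(l1²+l2²)], which equals 1 under sphericity and is at least 0.5 with three visits.
- 0.8/0.2: l = 0.2 and 1.0; ε = 1.44/2.08 = 0.69.
- 0.7/0.3: l = 0.3 and 0.833; ε = 1.284/1.569 = 0.82.
- 0.6/0.3: l = 0.4 and 0.8; ε = 1.44/1.60 = 0.90.

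**True level of the interaction test at nominal 5%.** These are simulated null trials with 38 per arm, normal data and the same covariance in both arms. Repeat runs agreed within about 0.2 percentage points.

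| Assumed pattern (a/b) | ε | Uncorrected level |
|---|---|---|
| Spherical | 1.00 | 5.0% |
| 0.6/0.3 | 0.90 | 5.4% |
| 0.7/0.3 | 0.82 | 5.7-5.9% |
| 0.8/0.2 | 0.69 | 6.7% |
| 0.6/0.3, SD tripled at draw 2 | 0.63 | 7.0-7.2% |
| 0.8/0.2, SD doubled at draw 4 | 0.57 | 7.8-7.9% |

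Letting the correlation decay with time instead gives:
- gaps of 0.75 and 7 months, monthly correlation 0.6 to 0.95: ε 0.59-0.75, level 6.3-7.5%;
- gaps of 0.75 and 25 months, monthly correlation 0.8 to 0.9: ε 0.56-0.62, level 7.3-7.7%.

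Greenhouse-Geisser gave 4.6-5.2% throughout. Huynh-Feldt and the multivariate test gave 4.9-5.1%.

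**Ceiling.** At ε = 0.5 the statistic follows F(1,74) but is referred to the F(2,148) critical value of 3.057, so P[F(1,74) > 3.057] = 8.5%. For the within-arm time test (n = 38), P[F(1,37) > 3.120] = 8.6%.

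**What the named remedies do.**
- *Transformation.* Take lognormal fold changes with exchangeable log-scale correlation 0.5 and visit levels of 2, 1, 1 or 3, 1, 2. Raw-scale ε is 0.76-0.82 and log-scale ε is 1.0, so logging removes the part tied to the mean. If the log-scale correlations themselves fade with time, ε stays below 1 after logging.
- *Nonparametric.* The usual rank counterpart (Friedman) compares visits within subjects and has no group-by-time term. Taking that route loses the test in question.

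**The case against.** The case against has real force on several points.

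- **The covariance is unknown.** A reader might infer that the interaction test is known to exceed 5%. The documents do not support that, because they report no correlations. Closeness in time is also not the only driver: draw 2 precedes chemotherapy, draw 3 follows one cycle and draw 4 is off treatment, so draws 2 and 3 may be less alike than their spacing suggests. This stands, and the levels above are conditional.
- **A transform can help.** A reader might infer that the plan's remedies are useless here. That goes too far. If a transform equalised the SDs and left the correlations alone, the 7.8-7.9% case would fall to 6.7% and the 7.0-7.2% case to 5.4%. What remains is the part due to correlation.
- **Assumptions will be tested.** The SAP says so, and a violation could be detected. The gap is that no dependable remedy follows, and the choice would be made after seeing the data.
- **The reach is limited.** A reader might infer that the trial's main comparisons are inflated. They are not. The group main effect, the t-tests for Hypotheses 2-4 and single-df linear or quadratic contrasts with their own error terms do not depend on sphericity. The interaction gates only descriptive within-arm follow-up in a pilot.

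These points limit the size of the problem. They do not supply the missing remedy.

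**Conclusion.** The point holds as a moderate one that should be fixed. The time and group-by-time tests rest on an assumption that the visit schedule makes doubtful, and the stated rule for violations does not reliably repair it. Under the assumed patterns the uncorrected interaction test runs at about 5.4% to 7.9%. The ceiling is about 8.5% for the interaction and 8.6% for the within-arm time tests. These figures assume normal data, equal covariance in the arms and 38 per arm. If sphericity happens to hold, the level is 5%.

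**What to change.** Add to SAP 2.7, and to the matching text in Protocol item 10, that all RMANOVA time and group-by-time tests, including the within-arm follow-ups, use Greenhouse-Geisser corrected degrees of freedom whatever any sphericity pre-test shows. A Huynh-Feldt correction, a multivariate test, or a mixed model with unstructured visit covariance is equally acceptable if one is named in advance. State too that the nonparametric route does not replace the interaction test unless the chosen method has a group-by-time term.

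The cost is one or two sentences, and the correction is standard software output. The only statistical price is a very slightly conservative test, about 4.8% instead of 5%, when sphericity nearly holds.
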